7.6.8 Other Events of Special Interest

OEOSI will be summarized by treatment group for each category.

The following analyses will be conducted using the 100-day safety window:

- Overall summary of OEOSI by worst CTC grade (any grade, grade 3-4, grade 5) presented by Category / PT
- Overall summary of drug-related OEOSI by worst CTC grade (any grade, grade 3-4, grade 5) presented by Category / PT

A by-subject listing of OEOSI will be provided.

7.6.9 Multiple Events

The following summary tables will be provided:

- A table showing the total number and rate (exposure adjusted) of occurrences for all AEs.
- A table showing the total number and rate (exposure adjusted) of occurrences for AEs occurring in at least 5% of subjects in any treatment group.

A listing displaying the unique instances of all AEs, i.e., after duplicates have been eliminated and overlapping and contiguous occurrences of the same event (i.e. same PT) have been collapsed will be provided. No formal comparisons will be made between treatment groups.

7.6.10 Laboratory Parameters

The analysis population for each laboratory test is restricted to treated subjects who underwent that laboratory test.

7.6.10.1 Hematology

The following will be summarized by treatment group as worst CTC grade on-treatment per subject and as shift table of worst on-treatment CTC grade compared to baseline CTC grade per subject: hemoglobin (HB), platelets, white blood counts (WBC), absolute neutrophils count (ANC) and lymphocyte count (LYMPH).

The analyses will be conducted using the 30-day safety window.

A by-subject listing of these laboratory parameters will be provided.

7.6.10.2 Serum Chemistry

The following will be summarized by treatment group as worst CTC grade on-treatment per subject and as shift table of worst on-treatment CTC grade compared to baseline CTC grade per subject: ALT, AST, alkaline phosphatase (ALP), total bilirubin and creatinine.

The analyses will be conducted using the 30-day safety window.

A by-subject listing of these laboratory parameters will be provided.

7.6.10.3 Electrolytes

The following will be summarized by treatment group as worst CTC grade on-treatment per subject and as shift table of worst on-treatment CTC grade compared to baseline CTC grade per subject: sodium (high and low), potassium (high and low), calcium (high and low), magnesium (high and low), and Glucose Serum (fasting hyperglycemia and hypoglycemia regardless of fasting status).

The analyses will be conducted using the 30-day safety window.

A by-subject listing of these laboratory parameters will be provided.

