Laboratory Tests	X	On site/local complete blood count (CBC) w/differential, Chemistry panel including: LDH, AST, ALT, ALP, T-Bil, blood urea nitrogen (BUN) or serum urea level, creatinine, Na, K, Cl, total protein, glucose, albumin, amylase, lipase within 14 days prior to randomization. Urinalysis as clinically indicated within 14 days prior to randomization. Endocrine panel (TSH, Free T4, Free T3. Total T3/T4 are acceptable if free T3/T4 are not available), Hep B/C (HBV sAG, HCV antibody or HCV RNA), HIV (when required by local regulations), within 28 days prior to randomization.
Pregnancy Test (WOCBP only)	X	Serum or urine to be done at screening visit and repeated within 24 hours of first dose of study therapy
Efficacy assessment		
Baseline Tumor Imaging Assessment	X	See Section 5.4 After complete resection and within 28 days prior to randomization. Disease-free status should be documented.
IWRS		
IWRS entry	X	IWRS entries must be made as follows: For subject number assignment at the time informed consent is obtained Prior to dosing for study drug vial assignment (call should be made within 3 days prior to dosing)

Table 5.1-2: On-Treatment Procedural Outline (CA209577)

Procedure	Cycle 1 Day 1 (C1D1)	Each cycle on Day 1 (up to 2 days prior to dosing, unless indicated otherwise in the Notes)	Notes Each cycle duration is 2 weeks until 8 doses of nivo/placebo are complete. Remaining subsequent cycles are 4 weeks in duration Treatment is until recurrence or discontinuation from study for maximum treatment duration of 1 year
Safety Assessments			
Targeted Physical Examination	X	X	To be performed within 72 hours prior to dosing
Vital Signs	X	X	Including BP, HR, temperature, Obtain vital signs within 72 hours prior to first dose.
Weight and ECOG Performance Status	X	X	Within 72 hours prior to dosing See Appendix 1 for ECOG Performance Status scale
Adverse Events Assessment	Continuously		Assessed using NCI CTCAE v. 4.0.
Review of concomitant medications	X	X	
Laboratory Tests	X	X	Within 72 hours prior to each dose. Include CBC w/differential, LFT's, BUN or serum urea level, creatinine, Na, K, Cl, LDH, Glucose, amylase, lipase, TSH (with reflexive Free T4 and Free T3. Total T3/T4 are acceptable if free T3/T4 are not available.) ^a Note: Laboratory tests do not need to be repeated if performed within 14 days prior to first dose

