Baseline local laboratory assessments that should be done within 14 days prior to randomization include: CBC with differential, Chemistry panel including: LDH, AST, ALT, ALP, T-Bil, blood

urea nitrogen (BUN) or serum urea level, creatinine, Na, K, Cl, total protein, glucose, albumin, amylase, lipase, and urinalysis (as clinically indicated).

Laboratory assessments that should be done within 28 days prior to randomization include: endocrine panel (TSH, Free T4, Free T3; Total T3/T4 are acceptable if free T3/T4 are not available), Hepatitis B and C (HBV sAG, HCV antibody or HCV RNA), HIV (when required by local regulations (see [Table 5.1-1](#)).

Pregnancy testing for WOCBP should be done at screening, within 24 hours prior to first dose.

Serious AEs are to be collected as soon as the informed consent form is signed.

5.3.2 *On-Treatment Safety Assessments*

Subjects will be evaluated for safety if they have received any study drug. Adverse event assessments will be continuous during the treatment phase. Adverse events and laboratory values will be graded according to the NCI-CTCAE version 4.

The start and stop time of the study therapy infusions and any interruptions or infusion rate reductions should be documented.

On study local laboratory assessments should be done within 72 hours prior to dosing (laboratory tests should not be repeated if performed within 14 days prior to the first dose) to include; CBC w/differential, LFTs (ALT, AST, total bilirubin, alkaline phosphatase), BUN or serum urea level, creatinine, Na, K, Cl, LDH, glucose, amylase, and lipase prior to each dose. TSH with reflexive Free T4, Free T3 (Total T3/T4 are acceptable if free T3/T4 are not available), can be performed at Cycles 1, 4, 7, 10, 12, 14, and 16 ([Table 5.1-2](#)). Additional measures including non-study required laboratory tests should be performed as clinically indicated or to comply with local regulations. Laboratory toxicities (eg, suspected drug induced liver enzyme elevations) will be monitored during the follow-up phase via on site/local labs until all study drug related toxicities resolve, return to baseline or are deemed irreversible.

Pregnancy testing for WOCBP should be done every 4 weeks relative to dosing on Day 1 of Cycle 1 regardless of dosing schedule.

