7.6.10.4 Additional Analyses

In addition, further analyses on specific laboratory parameters will be performed by treatment group:

Abnormal Hepatic Function Test

The number of subjects with the following laboratory abnormalities from on-treatment evaluations will be summarized by treatment group:

- ALT or AST > 3 x ULN, > 5 x ULN, > 10 x ULN and > 20 x ULN
- Total bilirubin > 2 x ULN
- Concurrent (within 1 day) ALT or AST > 3 x ULN and total bilirubin > 2 x ULN
- Concurrent (within 30 days) ALT or AST > 3 x ULN and total bilirubin > 2 x ULN

The analyses will be conducted using the 30-day safety window.

A by-subject listing of these specific abnormalities will be provided.

Abnormal Thyroid Function Test

The number of subjects with the following laboratory abnormalities from on-treatment evaluations will be summarized by treatment group:

- TSH value > ULN and
 - with baseline TSH value \leq ULN
 - with at least one FT3/FT4 test value < LLN within 2-week window after the abnormal TSH test
 - with all FT3/FT4 test values \geq LLN within 2-week window after the abnormal TSH test
 - with FT3/FT4 missing within 2-week window after the abnormal TSH test.

- TSH < LLN and
 - with baseline TSH value \geq LLN
 - with at least one FT3/FT4 test value > ULN within 2-week window after the abnormal TSH test
 - with all FT3/FT4 test values \leq ULN within 2-week window after the abnormal TSH test
 - with FT3/FT4 missing within 2-week window after the abnormal TSH test

The analyses will be conducted using the 30-day safety window.

A by-subject listing of these specific abnormalities will be provided.

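### The laboratory tables in SAP 7.6.10 do not match the protocol's panels: amylase and lipase are scheduled throughout but not summarized, while calcium and magnesium are summarized but never scheduled

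*SAP*

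**What the plan says.** **SAP.** Section 7.6.10 opens by limiting the population for each test: it is "restricted to treated subjects who underwent that laboratory test". Four subsections follow.

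- 7.6.10.1 covers hemoglobin, platelets, "white blood counts (WBC), absolute neutrophils count (ANC) and lymphocyte count (LYMPH".
- 7.6.10.2 covers "ALT, AST, alkaline phosphatase (ALP), total bilirubin and creatinine".
- 7.6.10.3 covers sodium, potassium and glucose, together with "calcium (high and low), magnesium (high and low".
- 7.6.10.4 states that "further analyses on specific laboratory parameters will be performed by treatment group", and then describes liver and thyroid tests only.

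The first three ask for worst on-treatment grade, a shift from baseline grade, and a by-subject listing of the named parameters.

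**Protocol.** The screening panel (Table 5.1-1) includes "creatinine, Na, K, Cl, total protein, glucose, albumin, amylase, lipase within 14 days prior to randomization". The on-treatment and follow-up panels (Tables 5.1-2 and 5.1-3) both include "creatinine, Na, K, Cl, LDH, Glucose, amylase, lipase, TSH". Section 5.3.2 repeats the on-treatment list: "creatinine, Na, K, Cl, LDH, glucose, amylase, and lipase prior to each dose". Section 8.4.3 undertakes to summarize on-study chemistry by worst grade, and names it separately from liver and renal function.

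**The concern.** A laboratory table is informative when the test is done on a schedule in everyone, and much less so when only a chosen few are tested. The SAP appears to have this reversed for four analytes.

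The pancreatic enzymes are measured repeatedly in every treated subject under blinded conditions, so they allow a clean comparison of graded abnormalities between nivolumab and placebo. No laboratory output uses them. Calcium and magnesium have no scheduled visit, so their denominators would be formed by local practice or clinical suspicion, yet they are presented in the same tables as scheduled electrolytes.

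At stake is how complete and how readable the laboratory safety comparison is, not the efficacy conclusions.

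**Working it through.** No figure in the plan is in dispute, so the check sets the lists side by side.

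**Step 1: where each analyte appears**

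| Analyte | Screening (Table 5.1-1) | On treatment (Table 5.1-2, 5.3.2) | Follow-up (Table 5.1-3) | SAP 7.6.10.1 to 7.6.10.4 |
|---|---|---|---|---|
| Amylase, lipase | yes | yes, each dose | yes, FU1 | none of the four |
| Calcium, magnesium | no | no | no | 7.6.10.3 |
| Sodium, potassium, glucose | yes | yes | yes | 7.6.10.3 |

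Amylase and lipase are in 3 of 3 protocol panels and 0 of 4 SAP subsections. Calcium and magnesium are in 0 of 3 panels and 1 of 4 subsections. Elsewhere in the protocol the latter two appear by name only in the abbreviation list.

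**Step 2: how many enzyme values there would be.** Dosing runs from Cycle 1 to Cycle 17. SAP 6.1 treats laboratory values up to the first dose as baseline and later ones as on-treatment. The Cycle 1 pre-dose sample is therefore baseline, and Table 5.1-2 lets a screening sample from the preceding 14 days serve instead. The maximum number of scheduled pre-dose on-treatment values is 17 − 1 = 16. FU1 falls 30 ± 7 days after the last dose, that is day 23 to day 37, so it adds a value only if it lands inside the 30-day window used for these tables.

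**Step 3: whether the adverse event tables cover the enzymes.** Protocol 6.3 sends a laboratory abnormality to the adverse event or SAE form if it is clinically significant, meets the SAE definition, leads to interruption or discontinuation, or needs corrective therapy. Protocol 4.5.2 exempts Grade 3 or higher amylase or lipase abnormalities from delay when there are no symptoms or signs of pancreatitis. Protocol 4.5.5 likewise exempts isolated Grade 4 abnormalities of that kind from discontinuation. Such an elevation need not trigger the dosing route into the adverse event form. Without corrective therapy or an SAE, its recording depends on the investigator judging it clinically significant.

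**Step 4: where calcium and magnesium values could come from.** Protocol 5.3.2 allows non-study tests when clinically indicated or locally required. With the tested-only denominator, the table rows would describe that subset. A shift table also needs a baseline grade, and no protocol visit requires one.

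**Step 5: whether redaction explains the gap.** The SAP contents list shows four subsections under 7.6.10, and all four are readable. A blacked-out block lies between 7.6.12 and 7.6.14, outside the laboratory section.

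**The case against.** The strongest reply is that clinically meaningful pancreatic toxicity is already compared by arm. Adverse events are tabulated by treatment group and worst grade (SAP 7.6.5), with separate tables for those leading to discontinuation or delay (7.6.3, 7.6.4). Pancreatitis is a named category of other events of special interest (7.1.1.2), summarized by arm over 100 days (7.6.8). The protocol's enzyme rules are exemptions that turn on pancreatitis itself. This stands. A reader might infer from the missing laboratory rows that a pancreatic signal would never be compared by arm. The documents do not support that; the gap is confined to graded values not reported as adverse events.

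A reader might also infer that the calcium and magnesium percentages will be inflated. That is plausible but not shown. Some tests may be done because local rules require them, and the documents do not say how many values exist or why they were taken. Double-blinding also limits differential testing by arm, and the SAP states its denominator openly. Only those rows of 7.6.10.3 are in question; sodium, potassium and glucose are scheduled.

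Finally, Protocol 8.4.3 promises summaries by broad class and names no analyte, and other scheduled tests such as LDH and chloride are also not tabulated under 7.6.10. So omission alone is not a breach. What sets amylase and lipase apart is that the protocol gives them explicit exceptions in the dosing criteria, which shows that graded elevations were anticipated.

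**Conclusion.** The mismatch is confirmed and modest in consequence. Two scheduled enzymes, with up to 16 pre-dose on-treatment values per subject plus FU1 when it falls within 30 days, have no graded summary, shift table or listing under SAP 7.6.10. Asymptomatic elevations, including Grades 3 and 4, may therefore go without a comparison by arm. Two unscheduled analytes occupy rows whose denominator and baseline availability are unknown, so no size or direction of bias can be stated for them.

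The conclusion assumes that amylase and lipase were entered in the eCRF (Protocol 5.3.2 warns that some assessments may not be) and that the redacted SAP text does not contain a separate enzyme analysis. It bears on safety reporting only. DFS, OS, alpha and power are untouched, and the protocol's dosing rules are not questioned.

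**What to change.** 1. Confirm that amylase and lipase results are captured as data in the eCRF.
2. In SAP 7.6.10.2, add both to the worst-grade table, the shift table and the by-subject listing.
3. In SAP 7.6.10.3, move calcium and magnesium to a listing. Alternatively, keep the rows, show the number tested in each arm (and the number with a baseline value, for the shift table), and footnote that the protocol did not schedule these tests. The second option is reasonable if the sponsor prefers not to reduce reporting of safety data that may exist.

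The cost is a short SAP edit and a little more table programming. If step 1 is satisfied, no new data are needed.

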7.6.10.4 Additional Analyses

In addition, further analyses on specific laboratory parameters will be performed by treatment group:

Abnormal Hepatic Function Test

The number of subjects with the following laboratory abnormalities from on-treatment evaluations will be summarized by treatment group:

- ALT or AST > 3 x ULN, > 5 x ULN, > 10 x ULN and > 20 x ULN
- Total bilirubin > 2 x ULN
- Concurrent (within 1 day) ALT or AST > 3 x ULN and total bilirubin > 2 x ULN
- Concurrent (within 30 days) ALT or AST > 3 x ULN and total bilirubin > 2 x ULN

The analyses will be conducted using the 30-day safety window.

A by-subject listing of these specific abnormalities will be provided.

Abnormal Thyroid Function Test

The number of subjects with the following laboratory abnormalities from on-treatment evaluations will be summarized by treatment group:

- TSH value > ULN and
 - with baseline TSH value \leq ULN
 - with at least one FT3/FT4 test value < LLN within 2-week window after the abnormal TSH test
 - with all FT3/FT4 test values \geq LLN within 2-week window after the abnormal TSH test
 - with FT3/FT4 missing within 2-week window after the abnormal TSH test.

- TSH < LLN and
 - with baseline TSH value \geq LLN
 - with at least one FT3/FT4 test value > ULN within 2-week window after the abnormal TSH test
 - with all FT3/FT4 test values \leq ULN within 2-week window after the abnormal TSH test
 - with FT3/FT4 missing within 2-week window after the abnormal TSH test

The analyses will be conducted using the 30-day safety window.

A by-subject listing of these specific abnormalities will be provided.

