Pregnancy Test (WOCBP only)	X	See Note	Serum or urine within 24 hours prior to the initial administration of study drug, then every 4 weeks (\pm 1 week) regardless of dosing schedule
PK and Immunogenicity Assessments			
PK samples			
Immunogenicity blood sample			

Table 5.1-2: On-Treatment Procedural Outline (CA209577)

Procedure	Cycle 1 Day 1 (C1D1)	Each cycle on Day 1 (up to 2 days prior to dosing, unless indicated otherwise in the Notes)	Notes Each cycle duration is 2 weeks until 8 doses of nivo/placebo are complete. Remaining subsequent cycles are 4 weeks in duration Treatment is until recurrence or discontinuation from study for maximum treatment duration of 1 year		
Efficacy Assessments					
Tumor Imaging Assessment		See Section 5.4 . Every 12 weeks (\pm 7 days) from first dose of study treatment through 12 months or distant recurrence whichever comes first			
Exploratory Biomarker Assessments					
Outcomes Research Assessments					
FACT-E	X	See Note	Assessed following drug vial assignment and preferably prior to procedures at Cycles 1, 3, 5, 7, 9, 10, 11, 12, 13, 14, 15, 16, and 17 (\pm 2 days).		
EQ-5D	X	See Note			
Health Care Resource Utilization	X	See Note			
Study Drug					
IWRS Drug Vial Assignment	X	X	Vials may be assigned up to 3 days prior to first dose date		

Table 5.1-2: On-Treatment Procedural Outline (CA209577)

Procedure	Cycle 1 Day 1 (C1D1)	Each cycle on Day 1 (up to 2 days prior to dosing, unless indicated otherwise in the Notes)	Notes Each cycle duration is 2 weeks until 8 doses of nivo/placebo are complete. Remaining subsequent cycles are 4 weeks in duration Treatment is until recurrence or discontinuation from study for maximum treatment duration of 1 year
Dispense Study Treatment (Active drug or placebo - blinded)	X	X	
First dose to be administered within 3 calendar days of randomization, then every 2 weeks for 8 doses and every 4 weeks beginning at week 17 (2 weeks after the 8th dose). See Section 4.5.
 
For Cycles 1-8, subjects may have study drug administered up to 2 days before or 3 days after the scheduled dosing date. Subjects may be dosed no less than 12 days from the previous dose. For Cycles 9-17, subjects may be dosed within a +/- 3 day window.

^a TSH, Free T3, Free T4 (Total T3/T4 are acceptable if free T3/T4 are not available) should be performed prior to dosing at Cycles 1, 4, 7, 10, 12, 14, and 16

Table 5.1-3: Follow-Up Procedural Outline (CA209-577)

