7.1.1.3 Immune-Mediated Adverse Events (US Submission)

In order to further characterize AEs of special clinical interest, analysis of immune-mediated AEs (IMAE) will be conducted. IMAEs are specific events (or groups of PTs describing specific events) that include pneumonitis, diarrhea/colitis, hepatitis, nephritis/renal dysfunction, rash, endocrine (adrenal insufficiency, hypothyroidism/thyroiditis, hypothyroidism, thyroiditis, hyperthyroidism, diabetes mellitus, and hypophysitis), and other specific events, considered as potential immune-mediated events by investigator that meet the definition summarized below:

- those occurring within 100 days of the last dose,
- regardless of causality,
- treated with immune-modulating medication (of note, endocrine AEs such as adrenal insufficiency, hypothyroidism/thyroiditis, hypothyroidism, thyroiditis, hyperthyroidism, diabetes mellitus, and hypophysitis are considered IMAEs regardless of immune-modulating medication use, since endocrine drug reactions are often managed without immune-modulating medication).
- with no clear alternate etiology based on investigator assessment, or with an immune-mediated component

The list of MedDRA preferred terms used to identify IMAEs is revisited quarterly and updated accordingly. The preferred terms used for the selection at the time of the database lock by categories will be provided.

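### The SAP's thyroid table sorts abnormal TSH by free T3/T4 only, so permitted total T3/T4 results fall in the missing row, and low TSH with low hormone is not shown separately

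*SAP*

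**What the plan says.** **SAP 7.6.10.4 (Abnormal Thyroid Function Test)** counts subjects with on-treatment TSH above ULN and subjects with TSH below LLN. Each group is subdivided by baseline TSH and by free hormone after the abnormal test.

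- High TSH: one sub-row is "with at least one FT3/FT4 test value < LLN within 2-week window after the abnormal TSH test", a second takes subjects with no free value below LLN, and the third is "with FT3/FT4 missing within 2-week window after the abnormal TSH test".
- Low TSH: one sub-row is "with at least one FT3/FT4 test value > ULN within 2-week window after the abnormal TSH test", a second is "with all FT3/FT4 test values \leq ULN within 2-week window after the abnormal TSH test", and the third is again the missing row.

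Total T3/T4 is not mentioned in that section. The section uses the 30-day safety window and adds a by-subject listing.

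**The protocol** allows a substitute assay. Table 5.1-2, footnote a, reads "TSH, Free T3, Free T4 (Total T3/T4 are acceptable if free T3/T4 are not available) should be performed prior to dosing". Section 5.3.2 has "TSH with reflexive Free T4, Free T3 (Total T3/T4 are acceptable if free T3/T4 are not available". The follow-up schedule in Table 5.1-3 repeats that "Total T3/T4 are acceptable if free T3/T4 are not available". The amendment summary in SAP 2.4 also records the allowance and ties it to site capability.

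**The concern.** The table has no category for a result that the protocol permits. The substitution is planned and depends on what the site's laboratory can run, so it is not a protocol deviation. The protocol describes T3/T4 testing as reflexive to TSH, so the missing row ought to show where the follow-on test was not done. Under the literal rule it also collects tests done correctly with the permitted assay. A reader cannot separate the two, and the rows showing high TSH with low hormone, or low TSH with high hormone, come out too small.

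The second problem is the missing lower bound in the low-TSH block. Low TSH with low hormone is the pattern that would point to the pituitary. The SAP names pituitary disorders as a select adverse event subcategory (7.1.1.1) and hypophysitis as an immune-mediated event (7.1.1.3), but its thyroid laboratory table cannot show that pattern.

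At stake is how readable one safety summary is. No hypothesis test depends on it.

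**Working it through.** There is no stated figure to reproduce. The check applies the SAP's rules to every possible hormone result.

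**Inputs.** Row definitions come from SAP 7.6.10.4. Permitted assays come from Protocol Tables 5.1-2 and 5.1-3 and section 5.3.2. Take one FT3 and one FT4 result in the two-week window, each low (L), normal (N), high (H) or no free result (–). That gives 4 × 4 = 16 combinations.

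**Step 1: high TSH.**
- At least one value below LLN: 16 − 3 × 3 = 7.
- Neither hormone has a free result: 1.
- Remainder, no free value below LLN: 16 − 7 − 1 = 8.

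**Step 2: low TSH.**
- At least one value above ULN: 16 − 3 × 3 = 7.
- Neither hormone has a free result: 1.
- Remainder, no free value above ULN: 8.

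**Step 3: what the remainder under low TSH contains.**

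| FT3/FT4 | Combinations | Count |
|---|---|---|
| at least one low, none high | L/L, L/N, L/–, N/L, –/L | 5 |
| only normal values | N/N, N/–, –/N | 3 |

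So 5 of the 8 combinations in the row contain a low hormone, and the row does not separate them from the 3 that do not. These are counts of patterns, not of subjects. The high-TSH block has the mirror image: its remainder of 8 merges normal with high hormone.

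**Step 4: a subject with total hormone only.** Suppose TSH is above ULN, total T4 is below its own LLN, and no free test was run because the site cannot run one. In the SAP's terms this is –/–, the single combination in the missing row. A subject with no hormone test at all is also –/–. The two are indistinguishable in the table.

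**Step 5: size.** Let *s* be the share of subjects with abnormal TSH and an out-of-range hormone whose only result in the window is a total. The confirmed sub-row then shows (1 − *s*) of its proper count. The documents give no *s*. If it were assumed to lie between 10% and 30%, the sub-row would show 90% to 70% of the proper count. If *s* is the same in both arms, with confirmed rates *a* and *b*, then

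- ratio: (1 − *s*)*a* / (1 − *s*)*b* = *a*/*b*, unchanged;
- difference: (1 − *s*)(*a* − *b*), reduced in proportion.

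**The case against.** The strongest reply has four parts.

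1. *No abnormal TSH is lost.* All high-TSH and low-TSH subjects are counted whatever their hormone result, as are those whose baseline TSH was not abnormal on that side. Only the hormone sub-rows move. This stands.
2. *The SAP never says that total-only subjects are missing.* True. That follows from the free-hormone wording and the absence of any visible rule for totals. A programmer might handle it sensibly, but would have to invent the rule.
3. *The toxicity is reported elsewhere.* Select adverse events have thyroid and pituitary subcategories (SAP 7.1.1.1, 7.6.6). For immune-mediated events, "diabetes mellitus, and hypophysitis are considered IMAEs regardless of immune-modulating medication use" (7.1.1.3), and endocrine events are tabulated with onset and resolution (7.6.7). A reader might infer that pituitary toxicity goes unreported; these sections rule that out. They do rest on events being reported and, for immune-mediated events, on the investigator's assessment, so they do not replace a laboratory count. The by-subject listing helps with individual cases but does not correct the summary.
4. *The low-TSH label is accurate as written, and pooling total with free values would mix assays.* Both are fair. The label is correct but uninformative, and the second point argues for separate rows or a footnote.

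A reader might also infer that the rule hides a drug effect by undercounting mainly on nivolumab. The documents do not support this. Assay choice depends on the site, and the trial is randomized and double-blind, so similar proportional misclassification is expected in each arm (Step 5).

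**Conclusion.** The point holds as a small, correctable flaw in a descriptive table. Followed literally, SAP 7.6.10.4 places permitted total-only results with untested subjects and so understates the hormone-confirmed sub-rows. It also cannot show low TSH with low hormone. Overall TSH counts, efficacy, alpha and power are unaffected.

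The literal effect is limited to subjects with an abnormal on-treatment TSH and no free result in the two-week window. It does not extend to everyone at a site without a free assay. The conclusion assumes that no rule for total values sits in text that is not visible.

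The number affected cannot be computed. A reader might multiply assumed rates: 760 × 2/3 = 507 on nivolumab; 507 × 10% = 51 and 507 × 20% = 101 with high TSH; 51 × 10% = 5 and 101 × 30% = 30 at total-only sites. That range of 5 to 30 should not be quoted as missed confirmed cases. Neither rate is in the documents. It assumes that each subject had a total result in the window, it includes subjects whose hormone was normal, and it uses randomized rather than treated subjects.

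**What to change.** In SAP 7.6.10.4:

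- Where no free T3/T4 result exists in the window, classify total T3/T4 against its own LLN and ULN. Show these subjects in separate total-only rows, or footnote how many were classified this way.
- Keep the missing row for subjects with neither a free nor a total result.
- Under low TSH, split the non-high row into (i) at least one value below LLN and none above ULN, and (ii) all values within LLN to ULN. The 16 combinations then divide as 7 + 5 + 3 + 1. The same split under high TSH is optional, for symmetry.

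The cost is a few lines of SAP text and minor programming, with no new samples or visits. It presumes that the total values and their local reference limits are in the database, which should be confirmed. The one analytical downside is that total hormone is affected by binding proteins, which is why these subjects should stay identifiable.
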